6. CLINICAL ASSESSMENTS

6.1. Efficacy

6.1.1. Montgomery-Åsberg Depression Rating Scale (MADRS)

The MADRS [1] is a clinician-rated scale used to assess depressive symptomatology during the previous week. Subjects are rated on 10 items to assess feelings of sadness, lassitude, pessimism, inner tension, suicidality, reduced sleep or appetite, difficulty concentrating and lack of interest. Each item is scored on a 7-point scale. A score of 0 indicates the absence of symptoms, and a score of 6 indicates symptoms of maximum severity. Total scores range from 0 to 60, with higher scores representing more severe depression.

6.1.2. MADRS-6 Subscale (Core Symptoms)

The MADRS-6 is a 6-item subscale of the MADRS evaluating the core symptoms of depression – apparent sadness, reported sadness, inner tension, lassitude, inability to feel, and pessimistic thought. Total scores range from 0 to 36, with higher scores representing more severe core symptoms of depression.

6.1.3. MADRS-5 Subscale (Anhedonic Symptoms)

The MADRS-5 is a 5-item subscale of the MADRS evaluating the anhedonic symptoms of depression – apparent sadness, reported sadness, concentration difficulties, lassitude, and inability to feel. Total scores range from 0 to 25, with higher scores representing more severe anhedonia symptoms of depression.

6.1.4. Clinical Global Impression – Improvement (CGI-I)

The CGI-I scale [2] is a one item, clinician-rated scale that is used to rate total improvement or worsening of mental illness regardless of whether the clinician considers it to be a result of drug treatment or not. The subject is rated on a scale from 1 to 7, with 1 indicating that the subject is very much improved and 7 indicating that the subject is very much worse.

6.1.5. Clinical Global Impression – Severity (CGI-S)

The CGI-S scale [2] is a one-item, clinician-rated scale used to rate the severity of the subject's current state of mental illness compared with a subject population with TRD. The subject is rated on a scale from 1 to 7, with 1 indicating a "normal state" and 7 indicating "among the most extremely ill subjects".

6.1.6. Quality of Life Enjoyment and Satisfaction Questionnaire – Short Form (Q LES Q SF)

The Q-LES-Q-SF [3] is a patient-reported, 16-item questionnaire designed to measure of the degree of enjoyment and satisfaction experienced by subjects in various areas of daily

functioning. Each item is scored from 0 (very poor) to 5 (very good). The total raw score is the sum of the first 14-items, ranging from 14 to 70. The raw total score is transformed into a percentage maximum possible score using the following formula:

$$\frac{(\text{raw total score} - \text{minimum score [14]})}{(\text{maximum possible raw score [70]} - \text{minimum score})}.$$

The percent of maximum score ranges from 0% to 100%, with higher scores represent better quality of life.

6.1.7. Sheehan Disability Scale (SDS)

The SDS [4] is a 3-item patient-reported questionnaire used to evaluate impairments in areas of the subject's life. The scale evaluates 3 domains: work, social life/leisure, and family life/home responsibility. Each domain is rated on an 11-point continuum (0 = no impairment to 10 = most severe). The total score is the sum of the 3 domains, ranging from 0 to 30, with higher scores representing greater disability.

6.1.8. Hamilton Rating Scale for Anxiety (HAM-A)

The HAM-A [5] is a 14-item, clinician-administered scale to evaluate symptoms of anxiety. Each item is rated on a five-point scale ranging from 0 (not present) to 4 (very severe). The total score is the sum of each item, scores range from 0 to 56, where higher scores representing greater severity of anxiety.

6.1.9. Massachusetts General Hospital Cognitive and Physical Functioning Questionnaire (CPFQ)

The CPFQ [6] is a 7-item, patient-rated scale used to measure cognitive and executive dysfunction in mood and anxiety disorders and was developed to assess clinically relevant cognitive and physical symptoms that could emerge or persist during long-term treatment for depression. Subjects grade the perceived quality of both their physical and cognitive functioning. The CPFQ is comprised of 7 distinct items: motivation/enthusiasm, wakefulness/alertness, energy, focus/attention, recall, ability to find words, and sharpness/mental acuity. Each item is scored from 1 (greater than normal) to 6 (totally absent). The total scores ranges from 7 to 42, with higher scores indicating worsening effects on cognition and physical functioning.

The CPFQ is comprised of two dimensions, physical and cognitive. The physical dimension assesses sleepiness and fatigue, and the cognitive dimension assesses apathy, inattention, forgetfulness, word-finding difficulties, and mental slowness.

6.2. Safety

Safety assessments include the evaluation of treatment-emergent adverse events (TEAEs), clinical laboratory test results, ECGs, vital sign measurements, and C-SSRS. Clinically significant physical examination findings are recorded as adverse events.

6.3. Adverse Events

The definitions, management of, and special considerations for AEs are provided in Section 10 of the protocol.

6.3.1. Clinical Laboratory Safety Assessments

The following clinical laboratory assessments are collected:

- Serum Chemistry: Albumin, total bilirubin, direct bilirubin, total protein, calcium, alkaline phosphatase, alanine aminotransferase, aspartate aminotransferase, blood urea nitrogen, creatinine, random glucose, sodium, potassium, and chloride.
- Urine Pregnancy Test: For females of childbearing potential. A test will be performed on site at each study visit.

6.3.2. Vital Signs

Vital signs include seated blood pressure, pulse, respiratory rate, and oral body temperature. Blood pressure is measured after the subject has been in a sitting position for 5 minutes. Height is only collected at Visit 1 and weight is collected at all study visits.

6.3.3. Electrocardiogram (ECG)

A 12-lead ECG is conducted after the subject has been resting (supine) for at least 2 minutes. At a minimum, the following parameters should be collected; PR interval, QRS duration, and QTcF.

The date and time of last dose prior to each ECG is recorded.

6.3.4. Columbia Suicide Severity Rating Scale (C-SSRS)

The C-SSRS [7] is a clinician-rated scale that reports the severity of both suicidal ideation and behavior. Suicidal ideation is classified on a 5-item scale: 1 (wish to be dead), 2 (nonspecific active suicidal thoughts), 3 (active suicidal ideation with any methods [not plan] without intent to act), 4 (active suicidal ideation with some intent to act, without specific plan), and 5 (active suicidal ideation with specific plan and intent).

If the subject reports active suicidal ideation, the C-SSRS captures information about the intensity of ideation, specifically the frequency, duration, controllability, deterrents, and reasons for the most severe types of ideation. Suicidal behavior is classified on a 5-item scale: 0 (no suicidal behavior), 1 (preparatory acts or behavior), 2 (aborted attempt), 3 (interrupted attempt), and 4 (actual attempt). More than 1 classification can be selected provided they represent separate episodes. For actual attempts only, the actual or potential lethality is classified for the initial, most lethal, and most recent attempts.

At all visits the C-SSRS is completed with a recall period since the last visit.

7. DEFINITIONS AND CONVENTIONS

7.1. General Considerations

Continuous data will be summarized using descriptive statistics: number of observations (n), mean, standard deviation (SD), median, minimum, and maximum. Frequencies and percentages will be used to summarize categorical (discrete) data. Presentations of categorical data will generally suppress percentages for items where the count is zero in order to draw attention to the nonzero counts. In general, mean, standard deviation (SD), median, minimum, maximum, and percentages will be presented with one decimal.

Data listings will present all data collected on case report forms (CRFs) by group, center, and subject number.

7.2. Subject Grouping

The study is enrolling two groups of subjects: Rollover Group (subjects who previously participated in Study AXS-05-TRD-201), and Direct Entry Group (subjects who had not previously participated in AXS-05-TRD-201). The Rollover Group will be further noted as “Rollover AXS-05” or “Rollover Placebo”. In general, data will be presented by Group (Rollover AXS-05, Rollover Placebo, and Direct Entry) and Overall.

7.3. Baseline

Unless otherwise stated, the last observed measurement prior to or on the date of enrollment will be considered the baseline measurement.

7.4. Analysis Populations

7.4.1. Safety Population

The Safety population will include all subjects who have received at least one dose of study medication. All safety analyses will use the safety population.

7.4.2. mITT Population

The modified Intent-to-Treat (mITT) population will consist of all who are enrolled, take at least 1 dose of study drug, and have at least 1 post-baseline efficacy assessment.

7.5. Data Quality Assurance

Accurate and reliable data collection is ensured by verification and cross check of the CRFs against the investigator's records by the study monitor (source document verification) and by the maintenance of a drug-dispensing log by the investigator. Collected data is entered into a computer database and subject to electronic and manual quality assurance procedures.

8. DESCRIPTION OF THE STUDY POPULATIONS

All tables, figures, and listings will include a population descriptor (e.g., mITT or Safety) in the titles.

8.1. Subject Disposition

Subject disposition summaries will be presented by group and overall. The summaries will include the number of subjects enrolled and the number of subjects in the safety and mITT populations, as well as the number and percentage of subjects who complete the study. The summaries will also include the reasons for early discontinuation from the study.

8.2. Demographics and Baseline Characteristics

A summary of demographics and baseline characteristics will be presented by group and overall for the Safety and mITT populations. The demographic characteristics will, at a minimum, consist of age, sex, ethnicity, and race using descriptive statistics.

Clinical baseline characteristics summarized for the Safety and mITT populations will include, at minimum, psychiatric history.

8.3. Medical History

A listing of medical history (both ongoing and past conditions) will be presented for the Safety population.

8.4. Prior and Concomitant Medication

All medications recorded on the CRFs will be coded using the WHO Drug Dictionary Version March 2021. Prior and concomitant medications will be summarized by group and overall for the Safety population by anatomical therapeutic chemical (ATC) Class Level 4 and WHO Drug base substance preferred name.

Prior medications are defined as medications with stop dates occurring before the date of first administration of any study treatment. Concomitant medications are defined as medications with start dates occurring on or after the date of first administration of any study treatment and no more than 30 days after the last study visit. Medications with start and stop dates that bracket the date of first administration of a study treatment will be summarized as both prior and concomitant medications.

Medications that were clearly stopped prior to the date of first administration of study treatment will be included in the prior medications table, and medications that were clearly started on or after the date of first administration of study treatment will be included in the concomitant medications table. All other medications will be included in both the prior and concomitant medications tables.

8.5. Identification and Summary of Protocol Deviations

Major protocol deviations will be summarized as far as they can be extracted from numeric or coded study data. All protocol deviations (major and minor) will be presented in a listing.

9. EFFICACY

This is a long-term and open-label safety study, and safety evaluation is the primary objective. The efficacy assessments are secondary and will be analyzed appropriately. Efficacy analyses will be performed on the mITT population.

9.1. Efficacy Variables

The following efficacy variables will be summarized by group and overall. Week 6 is the primary timepoint, and Weeks 1 and 2 are key secondary timepoints:

- Change from baseline in MADRS total score over time
- Percentage of subjects achieving clinical response on MADRS total score ($\geq 50\%$ improvement from baseline) over time
- Percentage of subjects achieving clinical remission on the MADRS total score (≤ 10) over time.
- Change from baseline in MADRS-6 score over time
- Percentage of subjects achieving clinical response on MADRS-6 score ($\geq 50\%$ improvement from baseline) over time
- Change from baseline in MADRS-5 score over time
- Percentage of subjects achieving clinical response on MADRS-5 score ($\geq 50\%$ improvement from baseline) over time
- Change from baseline on the CGI-S over time
 - [REDACTED]
 - [REDACTED]
- CGI-I over time
 - [REDACTED]
- Change from baseline in HAM-A over time. *The HAM-A was added during protocol Amendment 1, and therefore only subjects who have a baseline HAM-A will be included in this analysis.*

- Percentage of subjects achieving a response on the HAM-A ($\geq 50\%$ improvement from baseline) over time. *The HAM-A was added during protocol Amendment 1, and therefore only subjects who have a baseline HAM-A will be included in this analysis.*
- Percentage of subjects achieving remission on the HAM-A (≤ 7) over time
- Change from baseline in CPFQ over time. *The CPFQ was added during protocol Amendment 1, and therefore only subjects who have a baseline CPFQ will be included in this analysis.*
- Percent of subjects achieving an at least 1 category change from baseline in the CPFQ based on the following categories (*The CPFQ was added during protocol Amendment 1, and therefore only subjects who have a baseline CPFQ will be included in this analysis*):
 - ≤ 7 : Greater than normal functioning
 - 8–14: Normal functioning
 - 15–21: Minimally diminished functioning
 - 22–28: Moderately diminished functioning
 - 29–35: Markedly diminished functioning
 - 36–42: Totally absent functioning
- Change from baseline in Q-LES-Q over time
- Change from baseline in SDS total score over time
- Change from baseline in each SDS domain over time

■ [REDACTED]

■ [REDACTED]

■ [REDACTED]

■ [REDACTED]

- Percentage of subjects achieving remission on both the MADRS and HAM-A (MADRS total score ≤ 10 and HAMA total score ≤ 7) over time
- Percentage of subjects achieving remission on both the MADRS and SDS (MADRS total score ≤ 10 and SDS total score ≤ 6) over time

Unless otherwise stated, the changes will be derived in such a manner so that a positive change is indicative of improvement. For example, since the higher the MADRS, the greater impairment, the change for MADRS will be derived as baseline - post baseline. Change from baseline related variables will be analyzed using paired t-tests. Between treatment differences may be performed when appropriate (e.g., sufficient sample size).

10. SAFETY AND TOLERABILITY

Safety analyses will be performed for the Safety population. Safety evaluations will be based on the incidence, severity, relatedness, and type of adverse events, as well as on clinically significant changes in the subject's ECGs, vital signs, clinical labs, and C-SSRS.

10.1. Extent of Exposure

Summary statistics of exposure to study drug will be summarized for the Safety population. Exposure is defined as last dosing date – first dosing date + 1. The exposure will be summarized by summary statistics as well as by weekly frequency.

10.2. Adverse Events

Each AE and SAE term will be recorded as a verbatim term on the case report forms (CRFs). All AEs and SAEs will be coded by primary system organ class (SOC) and mapped to a preferred term using the MedDRA dictionary Version 22. The investigator will assess AE severity and relationship to the study treatment.

All AEs will be listed. However, only treatment emergent adverse events (TEAEs) will be included in the AE summaries. A TEAE is defined as any AE with an onset date in the interval between the first study treatment dosing date and 7 days after the last study treatment dosing date. In addition, any AEs occurring after the first dose that the investigators deem to be treatment related will also be considered TEAEs and will be included in the AE summaries.

For the purpose of calculating treatment emergence and inclusion in summary tables, incomplete onset dates will be imputed using the method described in [Appendix 1](#).

AEs will be summarized by the number and percentage of subjects in each primary SOC and preferred term. Subjects will be counted only once for each primary SOC and each preferred term. Summary tables of AEs by primary SOC, preferred term and severity will be provided. If a subject has more than one AE coded to the same preferred term, the subject will be counted only once for that preferred term by using the event with the highest severity. Similarly, if a subject has more than one AE within a primary SOC category, the subject will be counted only once in that SOC category by using the event with the highest severity. AEs by primary SOC, preferred term and relationship to study drug will be provided as well. In addition, serious adverse events (SAEs) by primary SOC and preferred term will be provided. Deaths and SAEs will be summarized similarly to AEs. All adverse event tables will also include the total number of events, counting multiple events per Subject.

In the AE summary, preferred terms within each SOC will appear in frequency order.

Frequencies for deaths and hospitalizations will also be summarized by treatment group and overall.

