## **10. ADVERSE EVENTS**

### **10.1. Definitions**

#### **10.1.1. Adverse Events**

An AE is defined as any untoward medical occurrence in a patient or clinical investigation subject administered a pharmaceutical product that does not necessarily have a causal relationship with the product. An AE can therefore be any unfavorable and unintended sign (including a new, clinically important abnormal laboratory finding), symptom, or disease, temporally associated with the product, whether or not related to the product.

Pre-existing diseases or conditions will not be considered AEs unless there is an increase in the frequency or severity, or a change in the quality, of the disease or condition. (Worsening of a pre-existing condition is considered an AE.)

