#### **10.1.6. Treatment-Emergent Adverse Events (TEAEs)**

An AE is defined as treatment emergent if the first onset or worsening is after an administration of study drug and not more than 7 days after the last dose. Any AEs that are deemed to be treatment related by the investigators will always count as TEAEs. The primary safety assessments will be based on TEAEs. For completeness, a listing of all reported AEs will be presented in the clinical study report (CSR).

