### **10.2. Management of Adverse Events**

Adverse events will be collected after administration of study drug through the End of Study (or Early Termination).

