### 10.2.3. Documentation

All AEs occurring within the period of observation for the study must be documented in the eCRF with the following information, where appropriate (the period of observation for the study is described in [Section 10.2.](#)):

- AE name or term.
- When the AE first occurred (start date).
- When the AE stopped (stop date or an indication of "ongoing").
- Severity of the AE.
- Seriousness (e.g., hospitalization or death).

- Actions taken.
- Outcome.
- Investigator opinion regarding the AE relationship to the study drug(s).

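### SAP 10.2 drops the protocol's worsening criterion from the definition of a TEAE, the event counted in the primary endpoint, without declaring a change

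*SAP*

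**What the plan says.** Protocol 10.1.6 gives the rule: "An AE is defined as treatment emergent if the first onset or worsening is after an administration of study drug", with an upper limit of 7 days after the last dose. It adds, with no time limit, that any AE the investigator judges treatment-related counts as a TEAE.

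SAP 10.2 gives another: "A TEAE is defined as any AE with an onset date in the interval between the first study treatment dosing date", with the window closing 7 days after the last dosing date. It then adds that "any AEs occurring after the first dose that the investigators deem to be treatment related will also be considered TEAEs". Worsening appears in neither sentence. The same section states that "only treatment emergent adverse events (TEAEs) will be included in the AE summaries"; other AEs are listed only.

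SAP 6.3 refers the reader back to the protocol: "The definitions, management of, and special considerations for AEs are provided in Section 10 of the protocol". That section contains 10.1.6, so the SAP points to one rule and writes out another. It nowhere says that the narrower rule is intended.

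**The concern.** Protocol 12.1.1 makes TEAE incidence the primary safety variable, so the TEAE rule fixes its numerator. The programmer must implement one rule, and the documents supply two. If SAP 10.2 is programmed as written, an AE that began before the first dose and worsened on treatment can appear in the AE listing yet be absent from every AE summary table, even though the protocol calls it treatment-emergent.

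Rollover subjects are the most plausible source. They come from Study AXS-05-TRD-201, and protocol 9.1.1 allows Day 1 to be combined with that study's final visit, so an event may be ongoing at the first dose here. SAP 7.2 reports the two Rollover groups separately from Direct Entry, so any omission would fall mainly in the Rollover columns.

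**Working it through.** Neither document states a TEAE rate, a number of worsening events or a precision target, so there is no planned figure to reproduce. The check applies both rules to each type of event.

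| Event | Protocol 10.1.6 | SAP 10.2 |
|---|---|---|
| Starts on treatment or within 7 days of last dose | Counts | Counts |
| Starts on treatment, then worsens | Counts | Counts |
| Pre-existing condition worsens on treatment; entered as a new AE dated at the worsening | Counts | Counts |
| Record with pre-dose onset; worsens on treatment; judged unrelated | Counts | Does not count |
| Same, judged related | Counts | Unclear: depends on whether it is taken to occur after the first dose |
| Record with pre-dose onset; no worsening; judged related | Counts, read literally | Does not count |

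The fourth row is a clear difference caused by the missing criterion, and the fifth is a possible one. The sixth comes from the treatment-related clauses, which also differ.

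**Can a record with a pre-dose onset exist?** SAP Appendix 1 provides for it. An onset with only a year, earlier than the year of first dose, is set to December 31 of that earlier year. An onset with month and year known, in an earlier month of the same year, is set to the last day of that month. Both dates fall before the first dose and fail the SAP's onset test. Appendix 1 has no step for a date of worsening.

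**Is a worsening date collected?** Protocol 10.2.3 lists a start date, described as when the event first occurred, and a stop date or an indication that the event is ongoing. It lists no worsening date.

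**Size per subject.** Planned enrolment is about 150 (protocol 12.2). If k subjects have such an event and no other TEAE, the protocol rule exceeds the SAP rule by 100 × k/150 percentage points:

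- k = 1: 100 × 1/150 = 0.67
- k = 5: 100 × 5/150 = 3.3
- k = 10: 100 × 10/150 = 6.7

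The values of k are assumptions, and k = 0 if every worsening is entered as a new dated record. A subject with another TEAE leaves overall incidence unchanged; only the system organ class, preferred term, severity and relationship rows for the omitted event could change. In a by-group column the unit is 100/n points, but the documents do not give n for any group.

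**The case against.** The best defence is that the two rules select nearly the same events under the protocol's own AE definitions. Protocol 10.1.1 states that "Pre-existing diseases or conditions will not be considered AEs unless there is an increase in the frequency or severity", or a change in quality. The condition is therefore not an AE until it worsens, and the AE naturally starts at the worsening. Protocol 10.2 collects AEs only once study drug has been given. The Schedule of Assessments has no AE entry at Visit 1, and the Visit 1 procedures list medical history but no AE recording. SAP 8.3 lists ongoing conditions under medical history. An event ongoing from the earlier study would then enter as history, and its later worsening would be a new on-treatment AE.

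Much of this stands, and it rules out two stronger readings. A reader might infer that the SAP omits all worsening of pre-existing conditions. The documents do not support that, because a worsening entered as a new AE counts under both rules. A reader might also infer that the primary result or a group comparison is materially distorted. No event rate supports that, and the SAP plans no between-group test of TEAEs; it mentions between-treatment differences only for efficacy.

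The defence does not close the gap. Treating events from the earlier study as history is an inference, since no text says so. Appendix 1 expressly handles AE onsets before the first dose. The eCRF completion guidelines mentioned in protocol 13.3.1 may settle the dating, but they are not supplied. The treatment-related clause cannot rescue a worsening judged unrelated.

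The sponsor may also say that protocol Section 12 leaves the derivation of variables to the SAP. It does, but the definition sits in Section 10, which SAP 6.3 refers to as the source, so a narrower rule should be declared as a change.

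**Conclusion.** The point holds as a minor inconsistency in the definition behind the primary endpoint. The difference in wording is certain. Its effect is confined to AE records with a pre-dose onset that worsen on treatment and are not captured by the treatment-related clause. The number of such records cannot be derived from the documents and is probably small: 0.67 percentage points of overall incidence per affected subject with no other TEAE, assuming 150 subjects in the Safety Population, and zero if sites always open a new record at the worsening. The SAP rule is not based on onset date alone, because its treatment-related clause offers a second route, but that route is worded more narrowly than the protocol's.

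**What to change.** 1. In SAP 10.2, define a TEAE as an AE that first begins or worsens after the first dose in this study and within 7 days of the last dose. Naming this study removes any doubt for Rollover subjects about which first dose is meant.
2. Before database lock, list AE records with a pre-dose onset and query sites about worsening on treatment. Have any such worsening entered as a new AE record with its own start date. The SAP sentence cannot do this alone, because no worsening date is among the listed AE fields.
3. Reconcile the treatment-related clause, which has no time limit in protocol 10.1.6 but covers only events after the first dose in SAP 10.2. If the narrower form is intended, state it as a deliberate change from the protocol.

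The cost is one or two SAP sentences, one listing and whatever site queries it raises. Reported TEAE incidence may rise slightly. If the listing is empty, the check confirms that nothing was lost.

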### **12.1. Study Endpoints**

#### **12.1.1. Primary Endpoints**

The primary safety variable is long-term safety as measured by the incidence of TEAEs following dosing with AXS-05.

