4.1. Sample Size Justification

This study planned to enroll approximately 150 subjects. This sample size allows for an assessment of the long-term safety and efficacy in patients with TRD.

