5. STUDY DURATION AND VISIT SCHEULE

Eligible subjects are treated with open-label AXS-05 for up to 15 months. The visit schedule is outlined in [Table 2](#).

Table 2: Schedule of Assessments

| Visit | V1 | V2 | V3 | V4 | V5 | V6 | V7 | V8 | V9 | V10 | V11 | V12 | V13 | V14 | V15 | V16 | V17 | V18 | V19 / ETV |
|---|-----------------|----------------|----------------|----------------|----------------|----------------|----------------|----------------|----------------|----------------|----------------|----------------|----------------|-----------------|-----------------|-----------------|-----------------|-----------------|-----------------|
| Study Day/Week | D1 ^f | Wk 1 (± 2d) | Wk 2 (± 2d) | Wk 4 (± 3d) | Wk 6 (± 3d) | Mo 2 (± 7d) | Mo 3 (± 7d) | Mo 4 (± 7d) | Mo 5 (± 7d) | Mo 6 (± 7d) | Mo 7 (± 7d) | Mo 8 (± 7d) | Mo 9 (± 7d) | Mo 10 (± 7d) | Mo 11 (± 7d) | Mo 12 (± 7d) | Mo 13 (± 7d) | Mo 14 (± 7d) | Mo 15 (± 7d) |
| Informed Consent | X | | | | | | | | | | | | | | | | | | |
| Inclusion/Exclusion Criteria | X | | | | | | | | | | | | | | | | | | |
| Physical Examination | X* | | | | | | X | | | X | | | X | | | X | | X | |
| ECG ^d | X* | | | | | | X | | | X | | | X | | | X | | X | |
| Serum Chemistry | X* | | | | | | X | | | X | | | X | | | X | | X | |
| Vital Signs, Height/Weight ^a | X* | X | X | X | X | X | X | X | X | X | X | X | X | X | X | X | X | X | |
| Urine Pregnancy Test ^b | X* | | | X | | X | X | X | X | X | X | X | X | X | X | X | X | X | |
| MADRS | X* | X | X | X | X | X | X | | | X | | | X | | | X | | X | |
| CGI-I | | X | X | X | X | X | X | | | X | | | X | | | X | | X | |
| CGI-S | X* | X | X | X | X | X | X | | | X | | | X | | | X | | X | |
| HAM-A | X | X | X | X | X | X | X | | | X | | | X | | | X | | X | |
| CPFQ | X | X | X | X | X | X | X | | | X | | | X | | | X | | X | |
| Q-LES-Q-SF | X | X | X | X | X | X | X | | | X | | | X | | | X | | X | |
| SDS | X | X | X | X | X | X | X | | | X | | | X | | | X | | X | |
| C-SSRS | X* | X | X | X | X | X | X | X | X | X | X | X | X | X | X | X | X | X | |
| Study Drug Dispensation ^c | X ^e | X | X | X | X | X | X | X | X | X | X | X | X | X | X | X | X | X | |
| Study Drug Accountability | | X | X | X | X | X | X | X | X | X | X | X | X | X | X | X | X | X | |
| Concomitant Medications | X* | X | X | X | X | X | X | X | X | X | X | X | X | X | X | X | X | X | |
| Adverse Events | | X | X | X | X | X | X | X | X | X | X | X | X | X | X | X | X | X | |

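### TEAE incidence, the primary endpoint, is planned as percentages of all dosed subjects plus event counts, so figures for late or steadily accruing events will depend on retention and understate 15-month risk

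*SAP*

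**What the plan says.** Protocol 12.1.1 defines the primary endpoint: "The primary safety variable is long-term safety as measured by the incidence of TEAEs following dosing with AXS-05".

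SAP 10.2 sets the summary: "AEs will be summarized by the number and percentage of subjects in each primary SOC and preferred term". It adds breakdowns by severity and relationship, tables of SAEs, deaths and hospitalizations, a listing of all AEs, and the total number of events in every AE table. The TEAE window closes 7 days after the last dose, except for later events judged related.

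The denominator comes from SAP 7.4.1: "The Safety population will include all subjects who have received at least one dose of study medication". On duration, SAP 5 says: "Eligible subjects are treated with open-label AXS-05 for up to 15 months". Protocol 7.4 states that withdrawn subjects are not replaced.

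Exposure is handled separately in SAP 10.1: "Exposure is defined as last dosing date – first dosing date + 1". It is summarised by descriptive statistics and weekly frequency, with no link to AE incidence. Under SAP 7.2, in general, "data will be presented by Group (Rollover AXS-05, Rollover Placebo, and Direct Entry) and Overall".

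**The concern.** The study exists to describe safety over as long as 15 months, yet its primary endpoint is the one main outcome with no time dimension. Efficacy variables and weight-change categories are summarised over time (SAP 9.1 and 10.5), laboratory values by scheduled visit (SAP 10.3), and exposure by week (SAP 10.1). The TEAE tables do not separate an event in Week 2 from one in Month 13.

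A subject who stops at Week 2 stays in the denominator, and the TEAE window closes a week later. From then on that subject in effect counts as event-free. For events that arise throughout treatment or only late in it, the percentage is thus a mixture of risk and retention. If many subjects leave early, a low percentage for a late event could be read as low long-term risk when few subjects were observed long enough to show it.

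**Working it through.** **Nothing to reproduce.** SAP 4.1 gives a planned size ("This study planned to enroll approximately 150 subjects") without an event rate, precision target or dropout rate. Neither document states an expected TEAE rate. What follows is an illustration, not a trial estimate.

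**Inputs from the documents.** Maximum treatment is 15 months (SAP 5). The denominator is all dosed subjects (SAP 7.4.1). There is no replacement (Protocol 7.4).

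**Assumptions.** 15-month retention R is 80% or 40%. Dropout is exponential and unrelated to event risk, with monthly hazard μ = −ln(R)/15, which is 0.01488 at 80% and 0.06109 at 40%. The 7-day tail is ignored.

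**1. Steady accrual, true 15-month risk 20%.** Event hazard λ = −ln(0.8)/15 = 0.01488 per month.

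Expected crude proportion = λ/(λ+μ) × [1 − exp(−15(λ+μ))], where exp(−15(λ+μ)) = 0.8 × R.

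- R = 80%: 0.500 × (1 − 0.64) = 18.0%
- R = 40%: 0.1958 × (1 − 0.32) = 13.3%

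**2. Late events, 10% risk confined to Months 12 to 15.** λ = −ln(0.9)/3 = 0.03512 per month in that window. The share still on treatment at Month 12 is R^(12/15), or 0.8365 and 0.4804.

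Expected crude proportion = R^(12/15) × λ/(λ+μ) × [1 − 0.9 × R^(3/15)].

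- R = 80%: 0.8365 × 0.0978 = 8.2%
- R = 40%: 0.4804 × 0.0915 = 4.4%

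The second factor in each line is what an interval table would show with the number on treatment at Month 12 as denominator: 9.8% and 9.2%. Both are close to the true 10%. A Kaplan-Meier type estimate would remove the remaining gap under these assumptions.

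**3. Early events, 20% risk confined to Month 1.** λ = −ln(0.8) = 0.2231 per month in Month 1.

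Expected crude proportion = λ/(λ+μ) × [1 − 0.8 × R^(1/15)], which gives 19.9% and 19.4%.

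| Event pattern | True risk | Crude, 80% retained | Crude, 40% retained |
|---|---|---|---|
| Steady over 15 months | 20% | 18.0% | 13.3% |
| Months 12 to 15 only | 10% | 8.2% | 4.4% |
| Month 1 only | 20% | 19.9% | 19.4% |

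**4. Does a person-time rate solve it?** Under steady accrual, yes: 0.01488 × 1200 = 17.9 first events per 100 person-years at either retention.

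For Month 1 events, no. Expected time at risk per subject is [1 − 0.8 × R^(1/15)]/(λ+μ) + 0.8 × [R^(1/15) − R]/μ, or 10.85 and 7.95 months. The rates are 0.1986/10.85 × 1200 = 22.0 and 0.1942/7.95 × 1200 = 29.3 per 100 person-years. That is a spurious ratio of 1.33 where the crude percentages almost agree.

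**The case against.** The strongest reply is that the plan gives more than percentages. Every AE table carries an event count, exposure is tabulated by week, disposition is shown by group with reasons for early discontinuation, and all AEs are listed. A reader will see that follow-up varies and why. This stands as a correction to any claim that crude percentages are all that is planned. It does not close the gap: counts and exposure are never linked, and total exposure does not give time to first event by preferred term.

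A reader might also infer that the three groups will be compared misleadingly. The documents do not support that. The groups are displayed side by side, but no between-group AE comparison is planned; the sentence on between-treatment differences sits in the efficacy section (SAP 9.1). Nothing in either document predicts that retention will differ by group. The groups do differ in prior AXS-05 exposure, but in-study person-time would not correct for that.

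Nor is it generally true that more dropout makes the drug look safer. Protocol 7.3 allows withdrawal for intolerable AEs, and such subjects already count as TEAE cases.

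Large gaps can be produced by comparing mean follow-up of 6 and 12 months. With a first-event hazard of 1.0 per person-year, treating each as fixed follow-up, 1 − exp(−0.5) = 39% and 1 − exp(−1.0) = 63%, 24 points apart. Under constant dropout, those follow-up times need 15-month retention of about 11% and 63%. At a hazard of 0.3 the gap is 12 points (14% and 26%). Neither scenario has any basis in the documents.

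Finally, this is an uncontrolled, descriptive study. That makes the point a reporting improvement, not a design fault.

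**Conclusion.** The point holds in a limited form. The planned percentage is a valid description of TEAEs observed among dosed subjects, and it is adequate for events that cluster in the first month. It is not a retention-free estimate of 15-month risk. For steadily accruing events it understates that risk, by 2.0 points at 80% retention and 6.7 points at 40% when the true risk is 20%. For events confined to Months 12 to 15 it loses more than half of a 10% risk at 40% retention.

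These sizes rest on assumed event rates, assumed retention, exponential dropout and dropout unrelated to event risk. If retention proves high, the effect is small. The stronger inference, that the percentages cannot inform long-term safety at all, does not follow: the distortion depends on event timing and on retention, which the documents do not forecast. The change is cheap and worth making before database lock, so that the measure is not chosen after the results are seen.

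**What to change.** Keep the crude table. Add to SAP 10.2, for any TEAE, SAEs and common preferred terms, by group and overall:

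1. TEAEs by onset interval (for example to Week 6, then to Months 6, 12 and 15), with the number still at risk as denominator; or cumulative incidence of first event at fixed months with 95% confidence intervals; or both.
2. As a supplement, subjects with a first event per 100 person-years at risk. State that this assumes a roughly constant hazard and can mislead for early-onset events.

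Flag events whose onset date was imputed under SAP Appendix 1. That rule assigns the first-dose date when onset is wholly missing, or when only the year is known and it matches the first-dose year. Uncertain onsets could therefore pile into the earliest interval.

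The cost is some programming and a few extra tables. AE start dates (Protocol 10.2.3) and first and last dosing dates (SAP 10.1) are already collected. Design, sample size and conduct do not change. The added estimates still assume that dropout is unrelated to event risk, and the table notes should say so.
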